5.1.4 ST3P-UP Application

This mobile app based on both Android and iOS platforms will be deployed to all site investigators and their clinical team, as well as all mentors, advisors and transition coordinators. This app will provide access to decision support tools to enhance the transition experience of all patients as they see their provider. It will provide ready access to the 2014 National Heart, Lung, And Blood Institute [NHLBI] SCD clinical guidelines and ambulatory care clinical pathway for management of SCD according to genotype and age/gender. This app will also house the "Who, What, Where, When, Sickle Cell Transition Education Module" that can be deployed during clinic visits and other patient encounters to ensure that the appropriate educational content is made available to the EASCD patient. An important feature of this app is the "Reach Out" feature that allows the ST3P UP site PIs the ability to communicate amongst themselves within the protocol network to address specific clinical dilemmas and questions in close to real time. In addition, the ST3P UP app allows the Transition Coordinators the ability to communicate with ST3P-UP study participants to address questions that will facilitate adherence to study procedures and clinical appointments.

Table for Structured Transition Program [STE] Collaborative Change Package

A. Initiating a Transition QI Project

- ° Raise staff awareness of need for the Structured Transition Program
 - ✓ Introduction to Six Core Elements
- Establish a Transition team with identified roles
- ° Introduction to Quality Improvement Process
 - ✓ Develop an Aim statement
 - ✓ Understand the PDSA process
- ° Complete practice assessment or organizational assessment

B. Professional Education

- ° Webinar 1 Care Coordination: Starting a Transition Process
- Webinar 2 Care Coordination: Transition Preparation
- ° Webinar 3 Care Coordination: Transfer to Adult Care
- ° Webinar 4 Care Coordination: Integration into Adult Care
- Webinar 5 Care Coordination: Youth/Young Adult and Parent Engagement

C. Transition Policy

- ° Process developed for review of Transition Policy by patient/parent with transition team
- ° Process developed for sharing Transition Policy with all patients
- ° Communication with patients and family

D. Patient Tracking and Monitoring

- Process developed for tracking patients of transition age
- Options (paper checklist, excel, Redcap, EMR)

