10.3 Endpoints

10.3.1 Definition of Primary Endpoint

Acute care visits will be calculated for each EA-SCD participant as the average number of acute care visits over a24-month period. Acute care visits will also be calculated for each EA-SCD participant as the average number of acute care visits per year over the entire study as a secondary endpoint. Acute care visits may include, but are not limited to hospital admissions, ED, urgent care, day hospital, or infusion center visits. The calculations for these endpoints are below:

$$Months \ on \ study = \frac{(Off \ Study \ Date - Enrollment \ Date)}{30.4375}$$

$$Acute \ care \ visits \ per \ 24 \ months = \frac{Total \ \# \ acute \ care \ visits \ reported \ on \ study}{Months \ on \ study} * 24 \ months$$

$$Acute \ care \ visits \ per \ 12 \ months = \frac{Total \ \# \ acute \ care \ visits \ reported \ on \ study}{Months \ on \ study} * 12 \ months$$

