10.3.4 Definition of ST3P UP Application Usage

- Usage will be documented in two ways for each study subject (EA-SCD, mentor, and advisor):
 - o Frequency of contacts between subjects and transition coordinator
 - o Frequency of educational resource views
- Usage will also be documented on the investigator and transition coordinator level, as frequency of contacts between investigator and transition coordinator and contacts between investigators across sites within the project.

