10.5.4 Primary Analysis

To evaluate the impact of PM, the acute care utilization rate per year will be compared between the PM+STE and STE arms. This will be accomplished using generalized linear mixed model with a Poisson distribution-log link construct. The model will include fixed effects for baseline acute care visits per year, the stratification factor (large sites vs small sites) and treatment arm, and a random effect for clinical site. Corresponding 95% confidence intervals will be calculated for the estimated ACU rate in each treatment arm.

Supportive and sensitivity analyses will be conducted to include potential confounding factors such as urban versus rural sites, education level, older first degree relative with SCD, genotype, age at transfer to adult care, and type of receiving provider (primary versus specialty). Univariate models will be fit for each factor, and those identified to be individually prognostic will be included in a multivariable model, and backward elimination followed by forward selection will be used to identify factors that are independently prognostic and to establish a final base model. Finally, treatment arm will be added to the base model to evaluate the impact of the intervention adjusting for significant baseline factors.

Two analyses will be conducted to estimate the impact of differential accrual between arms over time: (1) An additional term of year of enrollment will be added to the GLMM as a categorical variable; (2) We will subset the analyses to EA-SCD who were contemporaneously enrolled. Comparison of the PM+STE and STE ACU estimates from this subset to those results including all enrolled with and without controlling for year of enrollment will provide a comprehensive assessment of the potential bias due to differential accrual between arms over time. ACU rate in the STE only arm will be compared to historical ACU rates which were used for the original power calculations. Although these are comparisons to historical controls, this will provide preliminary evidence using a robust sample size of the potential impact of the structure transition education.

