ST3P UP application usage will be analyzed descriptively in terms of number of contacts between study subjects and transition coordinators, transition coordinators and PIs, and between PIs. Additionally, the use of education resources in the application will be summarized descriptively for the study subjects. Associations between EA-SCD outcomes (particularly acute care utilizations) and contact frequency, will be analyzed similarly to the methods described above for the primary analysis, with treating the app usage as a continuous covariate. Additionally, application usage will be correlated with EA-SCD PROs (specifically TIP-RFT assessments) similarly to the methods described above, treating the app usage as a continuous covariate. For the analysis described about regarding application usage, this will be done in two ways: (1) including all subjects and, for subjects who did not use the application, usage would be equal to zero; (2) only including the subset of subjects who used the application and looking at the impact of amount of usage on outcomes.

Composite QI-validated scores of the Six Core Elements provided by the sites in 6-month intervals will be analyzed using linear mixed models for repeated measures. One goal of the QI analyses is to assess the convergence in scores between pediatric and adult practices. This will be accomplished with a model that includes baseline QI score, clinic (pediatric versus adult), time, and the provider by time interaction as fixed factors. Site will be included as a random factor to account for repeated observations over time. Importantly, the type of provider will also be evaluated. This will be accomplished using a similar model as described above but will use provider type: Pediatrician to Pediatrician; Pediatrician to Internist; Pediatrician to Med/Peds Specialist, Med/Peds specialist to Med Peds specialist as the treatment factor. Additionally, composite QI-validated scores will be compared with site self-reported scores for concordance over time. Provider satisfaction with transition services will be summarized descriptively.

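### The app-usage analysis in 10.5.5 sets no time order between usage and acute visits, so it can show a spurious association in either direction and should not be labelled as impact

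*Combined protocol and SAP*

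**What the plan says.** Section 10.3.4 defines usage for each study subject by two measures, the first being "Frequency of contacts between subjects and transition coordinator" and the second the frequency of educational resource views. It gives no measurement window and no denominator. Section 10.5.5 then describes usage by count: "ST3P UP application usage will be analyzed descriptively in terms of number of contacts between study subjects and transition coordinators".

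For the link with outcomes, 10.5.5 states: "Associations between EA-SCD outcomes (particularly acute care utilizations) and contact frequency, will be analyzed similarly to the methods described above for the primary analysis". In that model usage is a single term on a continuous scale. TIP-RFT and the other patient-reported outcomes are to be correlated with usage in the same manner. Each analysis is run twice: once on everyone, with non-users set to zero, and once "only including the subset of subjects who used the application and looking at the impact of amount of usage on outcomes".

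The primary model (10.5.4) is a "generalized linear mixed model with a Poisson distribution-log link construct", with baseline visits, site size, arm and a random site effect. Section 10.3.1 divides all visits reported on study by months from enrollment to off study, including "the average number of acute care visits per year over the entire study as a secondary endpoint".

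Two facts bear on who has contacts and why. Coordinators can use the app to "communicate with ST3P-UP study participants to address questions that will facilitate adherence to study procedures and clinical appointments" (5.1.4). Patients are encouraged to download it but need not do so (footnote f to the 6.3 calendar).

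**The concern.** Usage accrues after enrollment, partly by the participant's own choice, and over the same months in which the visits are counted. Nothing in 10.5.5 places exposure before outcome: no lag, landmark or time-varying coding. Three paths can then create an association where the app does nothing.

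- **Reactive contact (upward).** If an acute visit leads to a coordinator contact, the outcome generates the exposure.
- **Time on study (upward).** If usage is a raw count, it grows with follow-up. Longer follow-up also contains a larger share of time after transfer, when visit rates are higher.
- **Engagement (downward).** Patients who choose to use the app may also be those who keep appointments and have fewer acute visits.

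At stake is the reading of the coefficient. A neutral app and coordinator service could be reported as harmful or as protective, and the users-only result would carry the word *impact*.

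**Working it through.** The plan states no figure for this analysis, so there is none to reproduce. The checks below set the true effect of usage to zero.

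**1. Time on study, by hand.** Inputs: 2.1 visits/year at 16-18y and 4.2 at 19-21y (section 1.1), taken as pre- and post-transfer rates; transfer at month 9, the midpoint of 6-12 months. Assumed: 0.5 contacts per month, unrelated to visits.

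- Followed 12 months: 6 contacts; rate (9×2.1 + 3×4.2)/12 = 31.5/12 = 2.63 per year.
- Followed 36 months: 18 contacts; rate (9×2.1 + 27×4.2)/36 = 132.3/36 = 3.68 per year.

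The participant with three times the contacts has a rate 3.675/2.625 = 1.40 times as high, with no link at all. As contacts per month, both have 0.5. If follow-up runs from 30 to 48 months, the rates are 107.1/30 = 3.57 and 182.7/48 = 3.81, a ratio of 1.07. The path therefore needs a raw count, wide variation in follow-up and a rise in visit rate. Simulated false rejection at the 5% level with robust errors:

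| Usage measure, no link | Follow-up | Participants | Rejects |
|---|---|---|---|
| raw count | 3-48 months | 366 | 16-21% |
| raw count | 6-42 months | 537 | 33% |
| raw count | 30-48 months | 366 | 6% |
| contacts per month | 3-48 months | 366 | 6% |
| contacts per month | 6-42 months | 537 | 5% |

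**2. Reactive contact and engagement.** Null simulation: 537 participants, 14 sites, 2 years, 6 visits/year, 300 replicates, Poisson regression adjusted for log baseline visits and site. Person-level (frailty) variance is assumed to be 1.0. Rate ratio (RR) per SD of usage, and share of trials with robust p<0.05:

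| Assumed link | RR | Rejects |
|---|---|---|
| none | 1.00 | 7% |
| 10%, 25%, 50% of visits prompt a contact | 1.09, 1.22, 1.34 | 72%, 100%, 100% |
| engagement, log rate -0.1, -0.2, -0.3 per SD | 0.92, 0.83, 0.75 | 64%, 99%, 100% |
| 10% prompted and -0.2 | 0.95 | 37% |
| 25% prompted and -0.2 | 1.11 | 68% |

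Restricting to users (40% of participants) changed these ratios by at most about 0.02 and lowered the rejection rates. Baseline adjustment did not remove the bias in any run with a link. A rate alone does not cure reactive contact: with 30% of visits prompting one, a same-window rate still rejects in 95% of trials and a raw count in 100% (537 participants, 6-42 months).

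**3. Standard errors.** Section 1.1 gives 5.3 ± 8.5 visits/year at 21-25y. Variance/mean = 8.5²/5.3 = 72.25/5.3 = 13.6, and the implied frailty variance is (72.25 - 5.3)/5.3² = 66.95/28.09 = 2.4. With no link, model-based Poisson errors reject in 51% of trials at variance 1.0 and 62% at 2.4, split about evenly between directions. Robust errors return this to about 7%.

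**4. Does ordering help?** Separating the windows is not enough. Year-1 usage against year-2 visits moved the RR only from 1.22 to 1.18 (25% prompted) and from 0.83 to 0.85 (engagement -0.2). Adjusting also for visits in the exposure window is what works. With a 6-month landmark, 25% prompted and variance 1.0, rejection was 76% in the same window, 41% with the landmark alone, and 7% with the landmark plus early-visit adjustment. With 50% prompted it was 100%, 78% and 8%. At variance 2.4 and 50% prompted, 21% still rejected, against 90% in the same window. Under engagement confounding, 13-16% still rejected after the full adjustment.

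**The case against.** A reader might infer more: that the analysis is bound to show greater use going with more acute care, so that a neutral app would look harmful. The documents do not support that. No section says an acute visit prompts a contact; the stated purpose in 5.1.4 is answering questions that help with study procedures and appointments. App use is voluntary, so engagement can push the ratio below 1. With both paths present, the sign turns on parameters the documents do not give.

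The time-on-study path is also conditional. *Frequency* in 10.3.4 can be read as a rate, the outcome is already divided by months on study, and the planned follow-up of at least 6 months in pediatrics plus at least 24 in adult care would leave little of it. This stands in part: the descriptive sentence in 10.5.5 speaks of a number of contacts, and section 7.1 allows earlier exits.

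It is fair, too, that 2.2.4 states no hypothesis that usage lowers visits and that 10.5.5 mostly uses associational wording. Only the users-only sentence is causal. This limits the severity but leaves the undefined window, the missing time order and the standard errors untouched.

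**Conclusion.** The point holds as a defect of a secondary, non-randomized analysis. As written, usage and visits share the same follow-up, usage has no fixed scale, and the users-only coefficient is called impact. With no true effect this can produce an association in either direction; the simulated range was 0.75 to 1.34 per SD of usage. That range rests on assumed contact, engagement and frailty parameters. With no link, and usage taken as a rate, the estimate centres on 1.00, so neither a false result nor its direction is certain. The simulations used Poisson regression with robust errors rather than the planned mixed model, so the rejection rates are indicative. The randomized comparison of STE+PM with STE is unaffected.

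**What to change.** Amend 10.3.4 and 10.5.5 as follows.

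- Express usage (contacts and resource views) as a rate per month on study.
- Order it before the outcome. Either relate usage in months 0-6 to visits after month 6, with person-time from month 6, or relate usage in each 3-month interval to visits in the next. The second keeps contacts made in adult care and matches the 3-monthly utilization collection in 6.4.3.
- In both, adjust for baseline visits and for visits up to the end of the exposure window.
- Use robust standard errors (clustered by participant in the interval version) or an overdispersion term.
- Treat TIP-RFT the same way: earlier usage, later score, adjusted for the score at the end of the exposure window.
- Replace *impact* with *association*, and state that confounding by engagement remains.

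The cost is SAP wording and no new data, provided the app records are dated, which the documents do not say. Early visits and early leavers drop out of this analysis. The 6-month landmark uses essentially only pre-transfer contacts, because participants spend at least 6 months in pediatrics. Adjusting for early visits may also remove part of any genuine early benefit.

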5.1 Study Intervention

5.1.1 Implementing a Structured Education Based Health Care Transition Quality Improvement Process [STE] within pediatric and adult SCD clinics

This intervention will involve incorporating the Six Core Elements of Health Care Transition into the pediatric and adult SCD clinics at each clinical site using quality improvement strategies. There will be 14 clinical sites enrolled in this trial. Each site is comprised of a pediatric SCD clinic, and adult SCD clinic and their partner CBO. Buy-in from both the adult and pediatric clinical leadership and the community has been obtained.

A study kick-off meeting will be held to orient all investigators, patient partners and research team to study procedures and to begin training on the QI process. Each of the 14 clinical sites and their corresponding CBOs will be provided funds to purchase a HIPAA compliant electronic tablet to facilitate education and training of site staff, stakeholders and study participants.

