5.3.6 Health Care Transition (HCT) Process Measurement Tool

To determine the level of improvement in a practice with adherence to the Six Core Elements, each pediatric and adult practice will be scored according to whether some or all of the implementation steps have been completed using the HCT Process Measurement Tool developed by GotTransition.org. Scores for each step will vary depending on complexity or importance. Each practice will be scored every six months to determine the degree to which they move closer to adherence to the desired standardized clinical practice pattern.

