10.3.5 Definition of Site-Level Endpoints

Health Care Transition Feedback Survey for providers:

• Provider satisfaction with transition services will be collected using a standard 5-point Likert scale.

Health Care Transition Process Measurement Tools:

- For Transitioning Youth to Adult Healthcare Providers (pediatric clinics)
- For Integrating Young Adults to Adult Healthcare Providers (adult clinics)

These elements of healthcare transition will be captured longitudinally for each site and will consist of the Core Elements of Health Care Transition. Scores will be self-reported by sites and then confirmed by the QI Coordinator. All Core Elements scores will be a

weighted sum of the individual items, and the overall HCT score will be a sum of the Six Core Element scores.

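### The QI convergence model adjusts for baseline score, so on the natural reading its clinic contrast does not estimate the pediatric-adult gap and it can miss change before month 6

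*Combined protocol and SAP*

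**What the plan says.** Section 10.5.5 states the aim: "One goal of the QI analyses is to assess the convergence in scores between pediatric and adult practices". The model for it is "a model that includes baseline QI score, clinic (pediatric versus adult), time, and the provider by time interaction as fixed factors". On the random part it says: "Site will be included as a random factor to account for repeated observations over time".

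The data come from the HCT Process Measurement Tool, which has a pediatric and an adult version. Section 5.3.6 says: "Each practice will be scored every six months to determine the degree to which they move closer to adherence". Section 6.1 shows a baseline score for both clinics and six-monthly scoring within a 60-month calendar. Section 5.1 says: "Each site is comprised of a pediatric SCD clinic, and adult SCD clinic and their partner CBO". With 14 sites, that is 14 pediatric and 14 adult clinics. Under Section 10.3.5, "the overall HCT score will be a sum of the Six Core Element scores".

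Section 10.5.5 leaves four things open:

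- whether the baseline covariate is the clinic's own score or a site-level score;
- whether the month-0 score is also in the response;
- which fitted quantity will be read as convergence;
- what provider means in the interaction, given that the main effect is clinic and the same paragraph goes on to a separate model for provider type.

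**The concern.** Convergence means that the difference between pediatric and adult scores moves toward zero. The baseline difference is where that path starts, so it is part of what is being measured. Baseline adjustment suits a comparison of randomised arms, where an initial difference is chance imbalance. Pediatric versus adult is not randomised, and here adjustment removes some or all of the initial gap from every later contrast.

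A reader of the adjusted clinic differences could see a gap growing while the practices were drawing level, or a difference near zero while a large gap persisted. Timing adds to this. Sections 1.2 and 5 aim for implementation within 18 to 24 months, so a good part of any change could come before the first follow-up score at month 6. If month 0 enters only as a covariate, the interaction cannot see that part.

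**Working it through.** The documents give no effect size, variance or power for the QI model, so there is no figure to reproduce. The check is algebra, followed by simulation under assumed values.

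**Identity.** Let G(t) be the pediatric-minus-adult difference in mean score at month t, and b the coefficient of the clinic's own baseline score. With baseline as a covariate and only post-baseline visits as outcomes:

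- clinic contrast at t = G(t) − b × G(0)
- interaction between two follow-up visits s and t = [G(t) − b × G(0)] − [G(s) − b × G(0)] = G(t) − G(s)
- contrast at month 6 = [G(6) − G(0)] + (1 − b) × G(0)

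The second line shows that the covariate leaves the interaction between follow-up visits unchanged. The third shows that the month 0 to 6 change enters only the level, mixed with what remains of the baseline gap.

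**Illustration.** Assumed: G(0) = 20, b = 0.7, so b × G(0) = 14. The simulations used site, clinic and error SDs of 5, 8 and 6, with fitted b of about 0.67 to 0.70. Many fits gave optimizer warnings, but the averages agree with the algebra.

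| True gap at months 0, 6, 12, 18, 24 | Adjusted gap at months 6–24, algebra | Simulated |
|---|---|---|
| 20, 0, 0, 0, 0 (closed by month 6) | −14 throughout | about −14, flat |
| 20, 20, 20, 20, 20 (never closes) | +6 throughout | about +6.5, flat |
| 20, 14, 10, 5, 0 (closes gradually) | 0, −4, −9, −14 | −0.1, −4.4, −9.0, −14.2 |
| 20, 24, 28, 33, 38 (widens) | 10, 14, 19, 24 | 10.7, 14.0, 19.3, 24.5 |

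In the first two rows the interaction is near zero both times, and the fully converged case shows the larger clinic difference. In the third row the gap closes while the adjusted difference grows. The fourth row trends the opposite way from the third, as it should.

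**Range over b.** A second simulation used an assumed starting gap of 16, eight follow-up visits, residual SD 4, site SD 3, baseline SD 10 and 60 replicates per case. Entries are fitted gaps from visit 1 to visit 8.

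| b | Gap closes 16 to 0: adjusted | Same data, no baseline covariate | Gap constant at 16: adjusted |
|---|---|---|---|
| 1.0 | −2.0 to −16.2 | +13.5 to −0.7 | 0.0 to −0.2 |
| 0.7 | +2.8 to −11.4 | +13.7 to −0.5 | +4.8 to +4.6 |
| 0.4 | +7.6 to −6.6 | +13.8 to −0.4 | +9.6 to +9.4 |

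For example, at b = 0.7 and visit 1: 14 − 0.7 × 16 = 2.8. The baseline gap is fully removed only at b = 1. At b = 0.4 the adjusted difference crosses zero instead of widening steadily. In the closing case the interaction was −2.03 per visit at every b, with or without the covariate.

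**Other readings of the text.**

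- *Site-mean baseline as covariate* (b = 1): the closing gap is fitted as +13.4 to −0.05, so the gap is preserved.
- *Month 0 both outcome and covariate*: the early change enters the interaction, but the level is still shifted. The fitted clinic term at month 0 was 0.0, +4.2 and +8.5 at b = 1, 0.7 and 0.4, against a true gap of 16.

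**The case against.** The strongest reply is that convergence is a change in the gap, the plan includes an interaction with time, and a time-constant covariate does not alter that interaction. From the same starting gap of 16, closing and widening gave −2.03 and +1.97 per visit (standard error about 0.22 in one simulated dataset). Read against the sign of the observed baseline gap, the interaction gives the direction of later change. Adding back b times the observed baseline gap also recovers the raw gap: in the closing case at visit 8 with b = 1 this returned −0.7, the same as the unadjusted fit. Section 10.5.5 does not say that adjusted clinic means will be the convergence output, nor that the covariate is clinic-level.

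Most of this stands, and it limits the point. A reader might infer that true convergence and true divergence give the same fitted result. The documents do not support that in general. Matching pairs can be built: gaps of 20, 14, 10, 5, 0 and of 0, 0, −4, −9, −14 differ by exactly 14 = 0.7 × 20 at every follow-up visit, so their adjusted paths coincide. But such a pair needs different starting gaps. The trial observes one starting gap, and in a rerun of this pair the observed baseline gaps averaged 19.9 and 0.2, which separates the two at once.

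Two things remain. The plan does not say that the baseline gap will be reported beside the interaction, or that the interaction must be read against its sign. And if month 0 is only a covariate, the interaction does not contain the change before month 6, even with the starting gap held the same.

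**Conclusion.** The point holds in limited form. It rests on two readings that Section 10.5.5 does not settle: that the covariate is each clinic's own baseline score, which is the natural reading because each practice is scored, and, for the early-change part, that month 0 is not also an outcome. The identity G(t) − b × G(0) then follows without further assumptions. The sizes do not: the gaps, the SDs and b are all assumed. With a starting gap of 20 and b about 0.7, the adjusted level is displaced by about 14 points. With a starting gap of 16, the displacement runs from 6.4 (b = 0.4) to 16 (b = 1).

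It would go too far to say that the model cannot distinguish convergence from divergence: trends after month 6 from a common start are separated by the interaction, and the baseline means restore the raw gap. What is missing is a model and a stated contrast that answer the named question directly. Section 2.3 lists adherence to the Six Core Elements as exploratory. No arm comparison, primary endpoint or patient-reported outcome is affected.

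**What to change.** For this non-randomised clinic comparison, amend Section 10.5.5 as follows:

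- Remove baseline QI score as a covariate and enter it as the month-0 outcome.
- Fit clinic, time (0, 6, 12, ...) and clinic-by-time, replacing the provider-by-time term.
- Use random effects for site and for clinic within site. Site alone is not enough once baseline is dropped: in 150 simulated trials with a clinic SD of 8, the site-only model gave a standard error of 4.5 for the change in gap against a true SD of 3.1, and 3.2 against 3.8 for the baseline gap.
- Report the raw pediatric-adult gap at each visit and its change from month 0, with 95% CIs, and name that change as the measure of convergence.
- If the pediatric and adult tools have different maximum scores, put them on a common scale first. The documents do not say whether they do.

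The cost is a change of SAP wording. The scores are already collected at baseline and every six months.

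### The QI score model assigns repeated-measures correlation to site, but the unit scored repeatedly is the clinic, so the uncertainty of the pediatric-adult comparison is misstated

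*Combined protocol and SAP*

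**What the plan says.** Section 10.5.5 states the method: "Composite QI-validated scores of the Six Core Elements provided by the sites in 6-month intervals will be analyzed using linear mixed models for repeated measures". It gives the purpose as "One goal of the QI analyses is to assess the convergence in scores between pediatric and adult practices", to be met with "a model that includes baseline QI score, clinic (pediatric versus adult), time, and the provider by time interaction as fixed factors". I take the interaction to be clinic by time. The only random term is then given: "Site will be included as a random factor to account for repeated observations over time". No clinic-within-site term and no residual covariance is named. A second model replaces clinic with provider type, whose categories describe pediatric-to-adult pairings.

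The data structure is set out elsewhere. Section 5.1 says "There will be 14 clinical sites enrolled in this trial" and "Each site is comprised of a pediatric SCD clinic, and adult SCD clinic and their partner CBO". Section 5.3.6 says "Each practice will be scored every six months to determine the degree to which they move closer to adherence". The calendar in section 6.1 has separate rows for the pediatric and the adult clinic, running to month 60.

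The patient-reported outcome model, also in section 10.5.5, names two random levels: the site, and the subject nested in it.

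**The concern.** The site term is given the task of handling repeated observations, but a site is not scored repeatedly; its two clinics are. With a site intercept alone, two scores from one clinic have the same correlation as a pediatric and an adult score from that site. Any lasting difference between the two clinics at a site, beyond the average pediatric-adult difference, is treated as independent noise that averages out over scorings. It does not average out.

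The pediatric-adult comparison is made within sites, so its error bars depend on exactly this variance. Its average over follow-up could be reported as significant too often, and the standard error of the convergence term could be wrong in either direction. The outcome model in the same section includes the nested unit, so the QI model falls short of the plan's own practice.

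**Working it through.** The plan gives no QI variance, correlation or standard error, so there is no plan figure to reproduce.

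**Inputs**
- 14 sites × 2 clinics = 28 repeatedly scored units (section 5.1).
- T, post-baseline scorings per clinic: 24/6 = 4 (the 24-month horizon in section 5.1.2) to 60/6 = 10 (calendar, section 6.1).
- τ² is the clinic-within-site variance and σ² the residual variance, scaled so that τ² + σ² = 1, and ρ = τ²/(τ² + σ²). The documents do not give ρ; I assume 0.05 to 0.8.
- The model adjusts for the baseline score. Conditioning on one earlier score leaves clinic variance τ²(1 − ρ), which replaces τ² below.

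**Formulas (balanced layout)**
- The site-only model has 28T − 2T − 13 = 26T − 13 residual degrees of freedom. Thirteen of these are site-by-clinic, with expected mean square σ² + Tτ²; the rest have expectation σ². The estimated residual is therefore R = σ² + 13Tτ²/(26T − 13).
- Ratio of site-only to correct standard error:
  - time-averaged clinic contrast: √[R/(σ² + Tτ²)]
  - contrast at one time point: √[R/(σ² + τ²)]
  - clinic-by-time term with stable clinic effects: √[R/σ²]

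**Example: T = 10, ρ = 0.5.** σ² = 0.5 and adjusted τ² = 0.5 × 0.5 = 0.25. R = 0.5 + (130/247) × 0.25 = 0.632.
- Time-averaged: √(0.632/3.0) = 0.46
- Single time: √(0.632/0.75) = 0.92
- Interaction: √(0.632/0.5) = 1.12

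**Time-averaged contrast, baseline-adjusted.** Rejection rates are for a nominal 5% test with no true difference, 3,000 simulated data sets per setting, site fitted as indicator terms.

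| ρ | T = 4: ratio | T = 4: rejection | T = 10: ratio | T = 10: rejection |
|---|---|---|---|---|
| 0.1 | 0.87 | 9% | 0.73 | 16% |
| 0.25 | 0.76 | 15% | 0.57 | 27% |
| 0.5 | 0.65 | 20% | 0.46 | 37% |
| 0.8 | 0.59 | 25% | 0.40 | 45% |

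Across T = 4 to 10 and ρ = 0.05 to 0.8, the ratio runs from 0.40 to 0.93.

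**Single-time contrast:** 0.89 to 0.99 over the same range.

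**Clinic-by-time term**
- Stable clinic effects: 1.01 to 1.21 with baseline adjustment (simulated rejection 2% to 5%), and up to 1.8 without it.
- Clinic-specific slopes (T = 10, ρ = 0.5, total SD 1): ratio 0.91 with 7% rejection for a slope SD of 0.5 over follow-up; 0.68 with 18% for a slope SD of 1.0.
- Serial correlation (T = 10): 0.72 with AR(1) 0.5 and ρ = 0.25; 0.64 with AR(1) 0.6 and ρ = 0.
- The slope effect weakens with fewer scorings. In a separate set of runs, slope SD 1.0 gave 14% to 15% rejection at T = 10 and 10% to 12% at T = 8; no inflation was seen at T = 4.

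**Provider type as a site-level factor** (two levels split 7/7, 10 scores, site-only model): ratio 0.92 to 1.01, rejection 5% to 10%. Wald testing with 14 sites can explain an excess of that size.

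**The case against.** The strongest defence is that a repeated-measures mixed model commonly carries a within-unit residual covariance, so the text may be incomplete rather than wrong. This stands in part: such a covariance would solve the problem. But none is stated, the section names site as the term that handles repetition, and the outcome model is described with the same class name yet still lists its nested unit.

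A second defence is that the declared goal is convergence, which is the interaction, and that no test of the time-averaged difference or significance rule for QI scores is stated. This also stands in part. A reader might infer that the convergence test is generally too liberal. The documents do not support that: under stable clinic effects it is correct or conservative, and nothing in the plan shows how far clinic trends differ. Different speeds are nonetheless plausible, because each site's transition team runs its own QI work (section 6.6.2).

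A reader might also infer that the provider-type model fails in the same way. Its categories read as pairings, and each site is one pediatric-adult pair. Coded per site, provider type is a between-site factor for which a site intercept is roughly adequate. The problem would carry over only if provider type were coded per clinic.

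**Conclusion.** The concern holds, with a limited claim. The random term is at the wrong level for the stated data structure, and the standard error of the time-averaged pediatric-adult contrast is too small in every setting examined. The ratio is about 0.4 to 0.9, with rejection of about 9% to 37% for ρ of 0.1 to 0.5.

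It is tempting to say that the standard error is about half its proper size. After baseline adjustment that needs roughly 8 to 10 scorings and ρ near 0.4 to 0.5, and the documents give no variance that would establish it. For convergence, the direction of the error depends on whether clinic trends differ or scores are serially correlated.

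All sizes assume a balanced layout and an assumed ρ. Adoption of the Six Core Elements is an exploratory objective (section 2.3). The comparison of trial arms and the primary endpoint do not depend on this model.

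**What to change.** In section 10.5.5, name clinic nested within site as the repeated unit in the QI model. Keep the site random effect and add a random intercept and time slope for clinic, or state a within-clinic residual covariance. Use small-sample degrees of freedom such as Kenward-Roger. This matters even with the clinic terms in place: in a small simulation (150 data sets per setting, Monte Carlo error about √(0.05 × 0.95/150) = 1.8 points), a plain 1.96 cutoff still rejected 5% to 11% for the clinic contrast. State also whether provider type is coded per site or per clinic, and apply the same terms if per clinic.

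The cost is a sentence or two of text and no new data. Intervals for the average clinic contrast widen by the inverse of the ratio, for example 1/0.76 = 1.3 times at T = 4 and ρ = 0.25. With stable clinic effects, the interval for the convergence term stays the same or narrows.
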